Thus far, the use of branched thoracic endografts has been limited to patients deemed to be at high risk of open repair. This was necessary as a first step to determine that the technique can safely be performed prior to use in a patient who has an option of open repair. The distinction of who is, and who is not eligible for open repair, remains a subjective one. It is insufficiently discriminatory to divide patients into high or low risk, as a large number of patients with TAAA suffer from major medical comorbidities that put them at moderate risk. The above described studies of branched endovascular TAAA repair report post-operative mortality rates of 6% among over 330 patients who were deemed to be at high risk for open repair. This overall mortality rate is nearly half that of contemporary open case series, those procedures being done in presumably healthier patients. As such, it is our belief that there is genuine equipoise to utilize and study B-TEVAR among patients at both moderate and high risk of open repair. We would suggest that there are insufficient data to treat a low risk patient with a TAAA using B-TEVAR, as the effectiveness and durability of open repair are well established. In the absence of an accurate pre-procedure risk assessment tool, we feel it is appropriate to leave the distinction between low and moderate risk to the discretion of the treating surgeon. The protocol requires that the treating surgeon specify what clinical criteria it is in their judgment that puts the patient at moderate or high risk. These data may, in time, be useful in better developing pre-operative risk stratification for patients with TAAA. Studies such as this one are necessary to improve our understanding in this regard.

Another important area of interest is the treatment of patients who have had prior aortic surgery. As described above, a significant number of patients with TAAA have undergone some form of prior aortic surgery, whether open or endovascular. Re-operative surgery, whether after prior open or endovascular repair, is associated with increased morbidity. As such, it is these patients who may stand to benefit most from B-TEVAR. Each of the above described case series included patients who had prior aortic surgery. Among the 189 patients treated by [name], 18% had undergone prior thoracic aortic surgery, and 28% had undergone prior infra-renal aortic surgery. Among the 81 patients in [name] series, 47% had undergone prior aortic surgery. One of the significant benefits of B-TEVAR is that it allows for a significant degree of design flexibility and customization. In the longer term, when commercially available "off-the-shelf" stent grafts for TAAA are available to treat most patients, it is likely to be this specific design flexibility that will make B-TEVAR an important tool for the minority of patients with TAAA and unusual or complex anatomy. Furthermore, we anticipate that re-operative surgery is likely to become increasingly common as endovascular technology is used more often and our patients live longer. As such, we feel it is important to include such patients in this study. The interaction between existing endovascular devices or prior open repair and the B-TEVAR construct does add an additional layer of complexity, but, in our opinion, the risk of these interactions can be mitigated with careful case planning and patient selection. The case report forms will track such prior surgery, and this should allow subsequent analysis of the safety and effectiveness in such patients.

Patients who have had prior aortic surgery will consist of two groups, those with a remote history of prior aortic surgery as well as those undergoing a staged approach to long extent TAAA repair (e.g. Crawford extent 1 or 2.). Patients who have had remote prior aortic surgery are described above in the case series reported by Drs. Greenberg and Chuter. These are patients who have experienced a discrete aneurysm above or below a prior repair, and those with degenerative anastomotic pseudoaneurysms (excluding infected pseudoaneurysms) that occur remotely from the index aortic procedure.

The second group consists of patients with long extent TAAA in whom the optimal method of repair remains uncertain. The uncertainty can be due to either: an expectation that the patient may indeed be healthy enough to tolerate an open peri-visceral repair; or due to the concern that the patient is not healthy enough to tolerate long extent of aortic coverage required for B-TEVAR. In other words, a patient's suitability for B-TEVAR may be uncertain due to concern that they are not necessarily "high risk" enough to need B-TEVAR or due to concern that they are too high risk even for B-TEVAR. Patients with TAAA vary significantly in terms of their physiologic and medical condition at presentation. Comprehensive care of these patients requires individualized assessment of their fitness for repair.

[name] recently reported on a cohort of 10 Patients with extent 1 or 2 TAAA who underwent a staged hybrid repair. A TEVAR was performed without establishing a definitive distal seal. The patient was allowed to recover. At a mean time interval of 14 weeks, a second operation was performed. The patients were put on femoral-femoral bypass and the peri-visceral aorta was replaced using traditional open techniques, sewing the proximal anastomosis to the TEVAR as an "endovascular elephant trunk" type procedure. This hybrid technique has been devised to reduce the morbidity of open repair of long extent TAAA. Some patients who undergo this first stage TEVAR procedure, however, have a difficult time recovering and are thought to be at high risk of subsequent open peri-visceral repair. Such patients are potentially good candidates for a second stage B-TEVAR procedure.

Another subset of patients with TAAA appear quite frail at initial presentation. Such patients are clearly not candidates for open repair. Based on the data from Scotland reported above, nearly half of patients referred for TAAA are deemed ineligible for open repair. Furthermore, as has been described in prior reports on B-TEVAR and EVAR, the Dacron used in the Cook Zenith stent graft can induce an inflammatory reaction. The severity of this reaction appears to correlate with extent of aortic coverage as well as the size of the excluded aneurysm, as sac thrombosis and platelet activation combine to cause a severe consumptive coagulopathy. Peri-operative deaths have been attributed to this inflammatory reaction and consumptive coagulopathy in prior reports. Furthermore, staging the procedure for long extent of aortic coverage may help reduce the incidence of spinal cord ischemia. A single animal model has shown reduce SCI with a staged

approach, and some investigators are currently incorporating this into their practice. Incidence of any spinal cord injury was 13% among patients with Type 2 TAAA undergoing staged aortic coverage and 22% among those undergoing a single stage procedure. Those patients who do not tolerate the TEVAR procedure will undergo no further procedure and will be left incompletely treated. If the patient is not healthy enough to tolerate a TEVAR procedure, they cannot be expected to tolerate additional aortic coverage with B-TEVAR. For those who are able to go on to the second stage, the TEVAR stage may help reduce the morbidity of complete aortic coverage in a single sitting.

Staging the TEVAR to precede the B-TEVAR procedure can be both diagnostic and therapeutic. It serves to help clarify the patient's physiologic reserve to determine what, if any, second stage is optimal for that individual. Furthermore, regardless of whether the second stage is performed with open or endovascular technique, it is expected to result in a lesser physiologic stress than repairing the entire TAAA in a single stage. A staged approach may be the safest way for a frail patient with a long extent TAAA to be treated.

Patients will be enrolled in B-TEVAR study with a plan for 2 different pathways to treatment, either in single sitting or in a staged approach. For those patients in whom a staged approach is planned or considered, consent will be obtained and the patient enrolled prior to undergoing the TEVAR 1st stage of the procedure. These patients will be tracked with a separate follow up case report form at 1 and 12 months and annually to 5 years or until they undergo the second stage with a branched device, at which time their outcomes will be followed according to the routine case report forms. Some patients who undergo the 1st stage will not go on to have the second stage done with a branched graft. This could be due to the determination that they can indeed tolerate open repair, or due to a complex recovery after the 1st stage TEVAR. Such patients will be followed up to 5 years after enrollment. All patients who are enrolled will be followed and reported on. Patients who undergo the first stage, but not the second stage, will be reported as a sub-group of patients in the annual report.

All patients who undergo the first stage TEVAR will be treated with the same TX2 device that is in the B-TEVAR protocol. The specific peri-visceral device used for the second stage could be any one of the 5 device options, CMD, t-Branch, LP CMD or t-Branch or physician modified.

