### **13. Zenith Alpha Thoracic Endovascular Graft**

The Cook Zenith Alpha Thoracic Graft will be used to establish proximal and distal seal and fixation. It is a cylindrical endovascular graft consisting of proximal and distal components. The proximal component can be either tapered or non-tapered and may be used independently (for ulcers/saccular aneurysms or blunt thoracic aortic injuries) or in combination with a distal component. The stent grafts are constructed of woven polyester fabric sewn to self-expanding nitinol stents with braided polyester and monofilament polypropylene suture. Both components are fully stented to provide stability and the expansile force necessary to open the lumen of the graft during deployment. Additionally, the nitinol stents provide the necessary attachment and seal of the graft to the vessel wall.

To assist with alignment, the proximal component has an uncovered stent. For added fixation and sealing, the proximal component has an internal sealing stent with fixation barbs that protrude through the graft material. In addition, the bare stent at the distal end of the distal component also contains barbs.

On devices with diameters of 40-46 mm, the proximal sealing stent remains constrained to ensure alignment with the inner curvature of the aorta.

To facilitate fluoroscopic visualization of the stent graft, gold radiopaque markers are positioned on each end of the proximal and distal components. Gold markers are placed on stent apices at the proximal and distal aspects of the graft margins, denoting the edge of the graft material, to assist with deployment accuracy.

The device comes in an expanded range of sizes compared to the Cook TX2 graft. The Alpha Thoracic is indicated for use in aortic diameters from 15 to 42 mm. As such, the inclusion criteria of the study have been amended to include aortic diameters where the Alpha Thoracic device can be deployed according to its FDA approved instructions for use.

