#### **2. t-Branch Low Profile Endovascular Stent-Graft (Cook Medical)**

Both the Cook CMD and t-Branch devices can be manufactured using the standard stainless steel Z-stents and standard woven polyester fabric, or they can be manufactured in a low profile (LP) version. The LP version uses the same materials and manufacturing process used for the Cook Alpha thoracic endograft that is currently commercially available. The Z-stents are made of Nitinol

and the fabric is a thin polyester. In either case, the same device design is used. The LP version allows for a significant reduction in delivery sheath size, down to 18F from the current 20-24F. Smaller delivery sheaths will significantly expand the eligibility for patients with TAAA, particularly women. The LP device is more costly to manufacture, and as such will be reserved for patients with small iliac artery access.

3-8: Please see Section 4.1.2 for details.

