### 5.1 Eligibility Criteria

#### 5.1.1 Inclusion Criteria

All patients must meet all of the following inclusion criteria to be eligible for enrollment into this study:

1. Patient is  $\geq 18$  years of age
2. Patients who are male or non-pregnant female (females of child bearing potential must have a negative pregnancy test prior to enrollment into the study)
3. Patient or Legally Authorized Representative has signed an Institutional Review Board (IRB) approved Informed Consent Form
4. Patient is considered by the treating physician and a second attending physician experienced in the care of patients with aneurysmal disease to be at high risk of open surgical repair due to one or more major medical co-morbidities (i.e. CAD, CHF, COPD, CRI, advanced age, generalized deconditioning, or other.) with ASA of 3 or more.
5. The patient has reasonable expectation of surviving the B-TEVAR procedure and has a life expectancy of greater than 1 year as determined by the PI and a second attending physician experienced in the care of patients with aneurysmal disease.
6. The patient has a thoraco-abdominal aortic aneurysm where necessary visceral branch vessels (i.e. the celiac, superior mesenteric, inferior mesenteric, renal and/or dominant spinal arteries) arise from the aneurysm or seal zones necessary for on-label thoracic endovascular repair
7. Patient has a thoraco-abdominal aortic aneurysm that meets **at least** one of the following:
  - aneurysm  $\geq 5.5$  cm in diameter
  - aneurysm has increased in size by 0.5 cm in last 6 months
  - aneurysm is believed to be causing symptoms
8. Patient has sufficient arterial access (femoral and/or iliac) that will allow delivery of the endovascular device with or without the use of a surgical conduit.
9. Patient has suitable proximal (aorta) and distal (aorta or iliac) arteries to allow for adequate fixation and seal:
  - A. Non-aneurysmal proximal aortic seal zone:
    1. with a length of 25 mm of proximal seal in non-aneurysmal aorta, with or without coverage of the left subclavian artery,

2. with an outer wall diameter of no less than 15 mm and no greater than 42 mm, and
- B. Non-aneurysmal distal aortic or iliac landing zone:
  3. With a length of at least 15 mm,
  4. Aortic seal zone no less than 15 mm and no greater than 42 mm or Iliac seal zone with an outer wall diameter of no less than 8 mm and no greater than 23 mm.

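### The protocol fixes the first-stage graft as TX2 but sets seal-zone eligibility to the wider Alpha range, so staged subjects can qualify at diameters their mandated graft does not cover

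*Protocol*

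**What the plan says.** The stage-1 device is set in section 2.1.4, in the paragraphs on the single-stage and staged pathways: "All patients who undergo the first stage TEVAR will be treated with the same TX2 device that is in the B-TEVAR protocol". No exception is given. The next sentence lists the graft options for the second stage, including the low-profile versions.

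The proximal seal zone is limited by criterion 9 of section 5.1.1: "with an outer wall diameter of no less than 15 mm and no greater than 42 mm". The Protocol Summary (Anatomic Criteria) and section 3.0 give the same limits, and the distal aortic seal zone has the same diameter range.

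The origin of that range is explained in section 4.1.1, item 13, which first compares Alpha with TX2: "The device comes in an expanded range of sizes compared to the Cook TX2 graft". It then puts Alpha's own indication at 15 to 42 mm and draws the consequence for eligibility: "the inclusion criteria of the study have been amended to include aortic diameters where the Alpha Thoracic device can be deployed".

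The section on how device selection will occur (the second one numbered 4.0.4) says that all enrolled patients meet the same inclusion and exclusion criteria. It sets no separate diameter range for the staged pathway.

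Several places allow Alpha as well as TX2 for seal and fixation: section 4.0.2 for the custom device, the text and component list of section 4.1.1 for the physician-modified device, and item 13 itself. Section 4.0.1, the overview of the physician-modified construct, names only TX2 for the proximal seal.

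**The concern.** Eligibility and device use are two rules applied to the same subject, and here they were set from different grafts. The eligible diameters follow Alpha, and the stage-1 graft is TX2. A subject planned for staged repair whose seal zone lies where Alpha fits and TX2 does not meets criterion 9, but the only graft named for that subject's first operation does not cover the anatomy.

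An investigator following the text would then have to use a graft outside its own size range or depart from the written plan. Section 11.8 requires prior IRB and FDA approval for changes in, or deviations from, the investigational plan. What is at stake is a protocol that can be followed consistently and a clear record of what counts as a deviation in the staged pathway.

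**Working it through.** No arithmetic applies, because the protocol states no figure that depends on this point. The check sets the texts side by side.

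1. **Eligible diameters.** Criterion 9, section 3.0 and the Protocol Summary all give 15 to 42 mm.
2. **Alpha indication.** Item 13 of section 4.1.1 gives 15 to 42 mm. The two ranges are identical, as expected from the statement that the criteria were amended to fit Alpha.
3. **Alpha against TX2.** Item 13 says that Alpha has the wider range of sizes and gives this as the reason for the amendment. Sizes might in principle mean lengths, but the sentences that follow are about aortic diameter, so diameter is the natural reading. Had TX2 already covered 15 to 42 mm, the amendment would not have been needed on the ground stated.
4. **Consequence.** Some diameters are therefore eligible but outside the TX2 range. Whether they lie at the low end, the high end or both cannot be determined. The TX2 description (section 4.1.1, item 1) gives no diameters, and Appendix XI lists its instructions for use as previously submitted and not included.
5. **Who is exposed.** One set of criteria applies to everyone, so staged subjects can be enrolled at those diameters. Section 2.1.4 then assigns TX2 to every first stage.
6. **Does another section override the TX2 sentence?** Step 4 of section 6.1, which describes the staged procedure, names no stage-1 graft. Section 2.1.4 is therefore the only place that specifies it. It sits under Background and Rationale, but the surrounding text also sets the timing of consent, the case report forms and follow-up, so it works as an operating rule.
7. **Do diameter-reducing ties close the gap?** Sections 2.1.4 and 4.0.1 describe narrowing TX2 in the physician-modified repair. They do not describe it for the stage-1 procedure, and narrowing cannot extend a graft to larger diameters.

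**The case against.** The strongest reply is that 15 to 42 mm is a study-wide envelope and not an instruction to place any given graft at any diameter. Criterion 9 is headed by a requirement for arteries that allow adequate fixation and seal. A sizing worksheet is completed before treatment (section 6.1). The investigator decides case by case whether the anatomy is suitable and whether to stage the repair. The t-Branch already has narrower limits inside the envelope (section 4.0.3). In practice an investigator may well avoid a mis-sized graft.

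This lowers the likely practical effect but does not remove the conflict. Criterion 9 defines suitability by its stated limits. The t-Branch example also cuts the other way: where the protocol intends a device-specific limit it writes one, and it writes none for TX2 at stage 1.

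The reply is right about section 4.0.1. That is a summary, and section 4.1 says its purpose is to specify every component that might be implanted; the component list in 4.1.1 includes Alpha. Section 4.0.1 should be aligned for clarity but is not a second contradiction.

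A reader might infer more, and the protocol does not support it:
- **Small iliac access.** The lack of a low-profile graft at stage 1 may look like the same fault. But criterion 8 allows a surgical conduit, section 6.1 prefers a single stage where access is difficult, and no TX2 sheath size is given.
- **Primary safety endpoint.** Injury or blood loss at the stage-1 operation may seem to feed it. That endpoint counts events within 30 days of the B-TEVAR procedure, and follow-up starts at implantation of the modified device (section 6.5).
- **Data capture.** An extra case report form field may seem necessary. Section 6.3 already records product identifiers on the TEVAR procedure form.

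**Conclusion.** The point holds as an internal conflict. The protocol mandates TX2 for every first stage, sets eligibility to a range chosen because Alpha is wider than TX2, and makes no exception for staged subjects. This rests only on the protocol's own statement that Alpha has the wider range.

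The size of the conflict is unknown. Neither the TX2 limits nor the staged share of the 60 subjects is given, so the number affected cannot be estimated and might be zero. A reader might be tempted to say that each affected subject shifts the primary effectiveness proportion by 1/60, about 1.7 percentage points. That would require every mismatched subject to fail who would otherwise have succeeded, and a denominator of 60. Subjects who never reach the second stage are analysed separately (section 6.5). Type I endoleak and migration are components of the 12-month endpoint, and section 9.1.2 includes staged subjects. But that the stage-1 graft provides the final proximal seal is an inference, not something the protocol states. No effect on either primary endpoint is shown, and the planned sample size is not touched. The point merits correction because the texts conflict and the correction is cheap.

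**What to change.** Reconcile the stage-1 device sentence in section 2.1.4 with section 4.0.2, the text, component list and item 13 of section 4.1.1, and criterion 9 of section 5.1.1, so that the grafts permitted at stage 1 and the diameters at which a staged subject is eligible agree. Align the summary in section 4.0.1 at the same time. If criterion 9 is what changes, carry the change into section 3.0 and the Protocol Summary. Which text governs is for the sponsor to decide; this review takes no position on the graft or the diameter rule.

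The cost is a wording amendment in a few places, with the usual IRB and FDA submission. No change to the sample size, endpoints or data collection is needed on this account.

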### 3.0 INDICATIONS

Physician modified branched thoracic endovascular grafts (B-TEVAR) are indicated in subjects diagnosed with a thoraco-abdominal aortic aneurysm involving the peri-visceral abdominal aorta having vascular morphology suitable for endovascular repair, including:

- Adequate femoral and/or iliac access compatible with the required delivery system, with or without the use of a surgical conduit
- Between 1 and 5 target visceral arteries that require branch creation (including the celiac, superior mesenteric, inferior mesenteric, renal arteries, and/or a dominant spinal artery)
- All essential branch vessels have seal zones that are  $\geq 4$  mm in diameter
- Proximal and distal aortic +/- iliac seal zones as described below :
  - A. Non-aneurysmal proximal aortic seal zone:
    1. with a length of 25 mm of proximal seal in non-aneurysmal aorta, with or without coverage of the Left subclavian artery, and
    2. with an outer wall diameter of no less than 15 mm and no greater than 42 mm, and
  - B. Non-aneurysmal distal aortic or iliac landing zone:
    3. With a length of at least 15 mm, and
    4. Aortic seal zone outer wall diameter no less than 15 mm and no greater than 42 mm or
    5. Iliac seal zone outer wall diameter no less than 8 mm and no greater than 23 mm.
- No essential spinal artery that cannot be preserved with a branch

The target treatment population are patients with TAAA who are at high risk of morbidity or mortality with open surgical repair as determined at the discretion of the treating surgeon and by having an American Society of Anesthesiologists (ASA) classification of 3 or higher .

